### 3.3.1 Rationale for Ocrelizumab Dose and Schedule

The dosing schedule of ocrelizumab during the postpartum period is at the discretion of the treating physicians, in accordance with local clinical practice and local labeling (USPI; SmPC). As per the dosing regimen approved in the labeling, 600 mg ocrelizumab is to be given as IV infusion every 6 months. The first dose is given as two 300 mg IV infusions two weeks apart; and subsequent doses are given as single 600 mg IV infusions. For women where a decision not to administer a second 300 mg infusion is taken after enrolment, continuation in the study will be allowed. If women did not experience a serious IRR with any previous ocrelizumab infusion, a shorter (2-hour) infusion can be administered for subsequent 600 mg doses (Ocrelizumab SmPC, Ocrelizumab USPI).

### 3.3.2 Rationale for Subject Population

As the aim of this study is to evaluate breastmilk transfer of ocrelizumab and the corresponding pharmacodynamic effects in the infant, it will be conducted in women with CIS or MS (in line with the locally approved indications) aged 18–40 years who have planned to start or resume ocrelizumab after delivery, while breastfeeding for a minimum of 60 days.

Based on the average terminal half-life of 26 days (ocrelizumab USPI), ocrelizumab is expected to be eliminated from the body by approximately 4.5 months, with the longest terminal half-life recorded as 53 days in 1 woman. Considering the interpatient variability and the fact that ocrelizumab, as a fully humanized IgG1, is not expected to cross the placenta in the first trimester (Simister 2003; Palmeira et al. 2012), it is assumed that a potential fetal exposure is unlikely in women whose last ocrelizumab infusion was earlier than 3 months before LMP. Women who were exposed to ocrelizumab within 3 months of their LMP, or during pregnancy, will therefore be excluded to eliminate cases of potential fetal exposure to ocrelizumab that could confound the results of B-cell levels in the infant or the presence of ocrelizumab in breastmilk.

Women who have given birth to more than one baby (i.e., have had non-singleton births) are excluded, because such mothers might find it difficult to comply with study requirements, and might find it more difficult to reserve the amount of breastmilk needed for the sample. Therefore, their infants might receive a different amount of breastmilk, potentially confounding the B-cell level results.

Infants who are > 24 weeks of age at the mother's first postpartum dose of ocrelizumab will be excluded. Although the WHO recommends exclusive breastfeeding up to 6 months with continued breastfeeding along with appropriate complementary foods up to 2 years of age or older (WHO 2020a), these recommendations are not followed in most countries. Recent findings from the National Immunization Survey 2018–2019 in the United States show that the percentage of infants who are breastfed decreases from 58.3% at 6 months to 35.3% at 1 year (Centers for Disease Control and Prevention 2020a). The maximum maternal age is set at 40 years, as mothers in late childbearing age of  $\geq$  35 years (in particular primiparous mothers) have been shown to have the greatest risk of non-initiation of exclusive breastfeeding both at discharge and at 1 month postpartum, even though they had the antenatal intention to exclusively breastfeed (Kitano et al. 2016).

Women with current (positive hepatitis B surface antigen [HBsAg] results) or previous (positive hepatitis B core antibody [HBcAb] titers) hepatitis B infection are also excluded. Most guidelines recommend that patients treated with anti-CD20 therapies who have chronic hepatitis B should receive prophylactic treatment with appropriate antiviral drugs (EASL 2017; Terrault et al. 2018), and all antiviral drug labels do not recommend breastfeeding when taking the drugs.

Ocrelizumab—F. Hoffmann-La Roche Ltd 38/Protocol MN42989, Version 4 (United States)

In addition, infants with any abnormality that may interfere with breastfeeding or milk absorption, such as cleft palate and/or lip, congenital diaphragmatic hernia and esophageal atresia are excluded, given that the co-primary aim of this study is to evaluate the corresponding pharmacodynamic effects of potential ocrelizumab exposure through breastmilk. Infants who have had at least one documented brief resolved unexplained event (BRUE), are also excluded, because these potentially life-threatening events have an unknown impact on infant physiology and development, and may confound the interpretation of infant's growth velocity and development milestones in the first year. The term BRUE is defined by the American Academy of Pediatrics as an event occurring in an infant younger than 1 year when the observer reports a sudden, brief, and now resolved episode of ≥1 of the following: (1) cyanosis or pallor; (2) absent, decreased, or irregular breathing; (3) marked change in tone (hyper- or hypotonia); and (4) altered level of responsiveness (Tieder et al. 2016).

### 4. MATERIALS AND METHODS

### 4.1 STUDY PARTICIPANTS

This study will enroll at least 10 women with CIS or MS (in line with the locally approved indications) who are breastfeeding or planning to breastfeed.

### 4.1.1 Inclusion Criteria

The following criteria must be met for study entry:

- An Informed Consent Form (ICF) for participation of the maternal subject and her infant (for collection of blood, infant demographic and adverse event data) is signed and dated by the subject. Where applicable, the written ICF with respect to the infant is also signed and dated by the holder of parental rights as designated by the maternal subject
- Woman is able and willing to comply with the study protocol, according to the judgment of the investigator, in particular:
  - Woman is willing to breastfeed (either exclusively, or with formula supplementation) for at least 60 days after the first postpartum ocrelizumab infusion (this decision is to be taken prior to and independent from study participation)
  - Woman is willing to provide breastmilk samples before and after their first and, if applicable, second postpartum ocrelizumab infusion
    - Note: Exposure to ocrelizumab includes administration of an initial split dose of two 300 mg infusions (in 250 mL 0.9% sodium chloride) separated by 14 days for women initiating treatment with ocrelizumab, or a single 600 mg infusion (in 500 mL 0.9% sodium chloride) for women already on treatment with ocrelizumab.
- Woman is between 18 and 40 years of age at screening
- Woman has a diagnosis of MS or CIS (in line with the locally approved indications)

- Woman has delivered a healthy term singleton infant (≥37 weeks gestation)
- Infant is between 2–24 weeks of age at the time of the mother's first postpartum dose of ocrelizumab
- For women who received commercial ocrelizumab (OCREVUS) before enrolment: documentation that last exposure ocrelizumab occurred more than 3 months before the LMP (i.e., excluded a potential fetal exposure) and was given at the approved dose of 2×300 mg or 1×600 mg
- Woman agrees to use acceptable contraceptive methods or alternative methods during the study as described below and, if applicable, upon study treatment discontinuation, as defined by the local prescribing information (see Section 4.6.1).
  - The following contraceptive methods are considered acceptable (failure rate > 1% [Clinical Trial Facilitation Group (CTFG)]): progestogen-only oral hormonal contraception, where inhibition of ovulation is not the primary mode of action; male or female condom with or without spermicide; cap, diaphragm, or sponge with spermicide; combination of male condom with cap, diaphragm, or sponge with spermicide (double-barrier method).

Birth control methods that are highly effective (i.e., failure rate < 1% [CTFG]) may also be used but are not required, and include: oral, intravaginal or transdermal combined hormonal contraception associated with inhibition of ovulation [unless not recommended or contraindicated during breastfeeding, see Table A2-1]; oral, injectable or implantable progestogen-only hormonal contraception associated with inhibition of ovulation; intrauterine device; intrauterine hormone-releasing system; bilateral tubal occlusion; vasectomized partner; sexual abstinence.

Note: lactational amenorrhea method can be used to ensure adequate protection from an unplanned pregnancy, and the following three criteria must be met:
1) amenorrhea; 2) fully or nearly fully breastfeeding (no interval of > 4–6 hours between breastfeeds); and 3) < 6 months postpartum. If any of the three listed criteria change at any stage during the study, an alternative or additional method of acceptable contraception is required. During the structured telephone interview, occurring every 2 weeks during the treatment and sampling period and every 3 months during the vaccination period, women will also be asked whether the three criteria are applied.

### 4.1.2 Exclusion Criteria

Mothers or infants who meet any of the following criteria will be excluded from study entry:

### Exclusions related to the mother

- Hypersensitivity to ocrelizumab or to any of its excipients
- Woman received last dose of ocrelizumab < 3 months before the LMP or during pregnancy (i.e., there was a potential fetal exposure to ocrelizumab)

- Active infections (note: the woman may be included once the infection is treated and is resolved; women with bilateral mastitis infection should not have samples collected until the infection is completely resolved)
- Prior or current history of primary or secondary immunodeficiency, or woman in an otherwise severely immunocompromised state. Woman may be re-screened and included if condition resolves
- Woman with known active malignancies, or being actively monitored for recurrence
  of malignancy including solid tumors and hematological malignancies (except basal
  cell and in situ squamous cell carcinomas of the skin). Women with high risk of
  breast malignancies undergoing prophylactic treatment with drugs such as
  tamoxifen are excluded
- Woman has history of breast implants, breast augmentation, breast reduction surgery or mastectomy
- Woman has prior or current history of chronic alcohol abuse or drug abuse
- Woman has any medical, obstetrical or psychiatric condition that, in the opinion of the investigator, would compromise the woman's ability to participate in this study
- Treatment with a DMT for CIS or MS during pregnancy and/or first weeks postpartum, with the exception of formulations of interferon-beta, glatiramer acetate or pulsed corticosteroids
- Drugs known to transfer to the breastmilk and with established or potential deleterious effects for the infant, including but not limited to aspirin (risk of Reye's syndrome), tetracyclines or fluoroquinolones. A more detailed, though not comprehensive, list can be found in Appendix 2
- Treatment with any investigational agent within 6 months or five half-lives of the investigational drug (whichever is longer) prior to the LMP, unless the investigational agent is ocrelizumab administered > 3 months prior to the LMP in the context of a study or registry sponsored by Roche

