### MS disease history:

- Date of MS symptom onset and MS diagnosis
- Disease status (as available): EDSS and number of relapses up to 1 year before the LMP
- History of previous DMTs (prior to and during pregnancy): number of DMTs ever used, last DMT before ocrelizumab
- Treatment history with ocrelizumab (to be collected only in women who received commercial ocrelizumab prior to enrolment): Documentation of start of ocrelizumab therapy and date and dose of last ocrelizumab infusion prior to enrolment.

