4.3 Demographic and Baseline Characteristics

4.3.1 Mothers

The following demographic, MS history, baseline disease characteristics of mothers will be summarized and listed in the FASM, unless otherwise stated:

Demographic and Baseline Characteristics

- Age at screening (years) as continuous and categorical (18 to ≤30, >30 to ≤35, >35 to ≤40, >40)
- Self-reported race and ethnicity
- Height (cm), weight (kg), and Body Mass Index (BMI: kg/m²)
- Smoking history (never, current, former)
- If previous smoker, time (years) since last use

- Alcohol use history (never, current, former)
- If previous user of alcohol, time (years) since last use
- Number of weeks post-partum
- Fertility status (listing only)

Multiple Sclerosis History

- Medical condition (Relapsing Remitting Multiple Sclerosis [RRMS], Secondary Progressive Multiple Sclerosis [SPMS], Primary Progressive Multiple Sclerosis [PPMS], CIS)
- Duration (years) since onset of MS symptoms and its category (≤3 years, >3 to ≤5 years, >5 years to ≤10 years, >10 years to ≤15 years, > 15 years)
- Duration (years) since MS diagnosis and its category (≤ 3 years, >3 to
 ≤5 years, >5 years to ≤10 years, >10 years to ≤15 years, > 15 years)
- Expanded Disability Status Scale (EDSS) details up to 1 year prior to pregnancy
- Number of EDSS assessments and its category (0, 1, ≥2)
- Most recent EDSS score
- Change in EDSS score from last pre-baseline measurement (up to 1 year before LMP) to baseline

Multiple Sclerosis History - Relapse

- Number of relapses up to 1 year prior to pregnancy and its category (0, 1, 2, 3 and $\geq 4)$
- Women with relapses up to 1 year prior to pregnancy (Yes, No)
- Duration (months) since last onset of MS relapse prior to enrollment and its category (≤6 months, >6 and ≤12 months, >12 and ≤18 months, >18 months)

If the date of the relapse is completely missing or if only the year is available, the patient will be excluded from the analysis as appropriate. If the day is missing but the month is available, it will be imputed to the first day of the month.

Multiple Sclerosis History - Prior Disease Modifying Therapies Use

- Number of Disease Modifying Therapies (DMTs) used prior to pregnancy (1, 2, 3 and >3)
- Type of DMTs used prior to pregnancy
- Number of DMTs used during pregnancy (1, 2, 3 and >3)
- Type of DMTs used during pregnancy
- Number of DMTs used post-partum but before baseline (1, 2, 3 and >3)

- Type of DMTs used post-partum but before baseline

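### No pre-LMP interval covers marketed B-cell-depleting antibodies other than ocrelizumab, so fetal exposure to one could enter the infant B-cell co-primary unflagged

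*Protocol*

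**What the plan says.** Three maternal criteria in Protocol 4.1.2 deal with earlier drug exposure. The synopsis and the Version 3 text carry the same wording.

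- Ocrelizumab: "Woman received last dose of ocrelizumab < 3 months before the LMP or during pregnancy" is an exclusion. Section 4.1.1 adds the matching inclusion condition.
- Investigational agents: "Treatment with any investigational agent within 6 months or five half-lives of the investigational drug (whichever is longer) prior to the LMP" is an exclusion.
- Any other DMT: "Treatment with a DMT for CIS or MS during pregnancy and/or first weeks postpartum" is an exclusion, "with the exception of formulations of interferon-beta, glatiramer acetate or pulsed corticosteroids". No period before LMP is attached.

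Section 3.3.2 gives the reason for the ocrelizumab interval: women exposed inside it "will therefore be excluded to eliminate cases of potential fetal exposure to ocrelizumab that could confound the results of B-cell levels in the infant". Section 3.1.2 states the aim for women resuming ocrelizumab as keeping fetal exposure from interfering with exposure through lactation. Section 1.3 describes rituximab as another anti-CD20 antibody and cites a study of 9 women with MS treated with it.

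On the analysis side, the intercurrent event for other DMTs (Protocol 6.5.1, SAP 4.4.1) covers use while breastfeeding, up to the B-cell measurement. SAP 4.4.4 re-admits samples taken outside the window or during illness. SAP 4.4.6 splits by first-dose regimen and type of feed. SAP 4.3.1 summarizes the types of DMT used before pregnancy and the time from last DMT to LMP, but no analysis of the co-primary uses them.

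**The concern.** The B-cell co-primary is meant to show whether exposure through milk depletes infant B cells. The protocol recognises that drug reaching the fetus would confound this, and removes the risk for ocrelizumab by an interval before LMP. The mechanism is not peculiar to ocrelizumab: another antibody against the same target, given close to conception, raises the same question. A woman who had such an antibody under routine care and then starts ocrelizumab postpartum is not caught.

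Appendix 1 first samples infant lymphocytes at Day 30, so there is no count before the infusion to show whether a low value was already present. The first infusion may fall at infant age 2 weeks, which puts the earliest Day 30 sample at about 6 weeks of age. A low count from fetal exposure would then be reported as a lactation finding. With about 10 infants, each one is 10 percentage points of the estimate.

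**Working it through.** **1. Which criterion catches which exposure before LMP**

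| Agent given shortly before LMP | Criterion in 4.1.2 | Excluded? |
|---|---|---|
| Ocrelizumab | Less than 3 months before LMP | Yes |
| Investigational B-cell-depleting agent | 6 months or five half-lives before LMP | Yes |
| Marketed or off-label B-cell-depleting agent other than ocrelizumab | DMT criterion starts at pregnancy | No named exclusion |

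Only the third row is open. The other-DMT intercurrent event does not reach it, because the drug was not taken while breastfeeding. Neither the sensitivity analysis nor the subgroups reach it.

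**2. The plan's precision figures (Protocol 6.2, SAP 2.2)**

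Two-sided Clopper-Pearson 95% limits with n = 10:

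- 1/10: 0.0025 to 0.4450, width 0.4425 (plan: 0.443)
- 2/10: 0.0252 to 0.5561, width 0.5309 (plan: 0.531)
- 0/10: upper limit 1 − 0.025^(1/10) = 0.3085 (plan: 0.31)

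The plan's figures reproduce to within 0.001 for the widths and to the stated two decimals for the upper limit.

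**3. Drug remaining in the mother**

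Inputs: half-lives of 26 days (average) and 53 days (longest recorded), both for ocrelizumab, from Section 3.3.2; no placental transfer expected in the first trimester, same section, with its end taken as LMP+91 days; term as 37 weeks, or 259 days after LMP, from Section 4.1.1. The documents give no half-life for another anti-CD20 antibody, so using ocrelizumab's is an assumption. A 20-day value is added to show the range.

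Fraction remaining = 2^(−days since dose / half-life).

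At LMP+91, a dose one day before LMP is 92 days old and a dose 91 days before LMP is 182 days old. At 37 weeks the first is 259 + 1 = 260 days old.

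| Half-life | Dose 1 day before LMP, at LMP+91 | Dose 91 days before LMP, at LMP+91 | Ratio | Dose 1 day before LMP, at 37 weeks |
|---|---|---|---|---|
| 20 days (assumed) | 2^(−92/20) = 4.1% | 2^(−182/20) = 0.18% | 22.6 | 2^(−260/20) = 0.01% |
| 26 days | 2^(−92/26) = 8.6% | 2^(−182/26) = 0.78% | 11.0 | 2^(−260/26) = 0.10% |
| 53 days | 2^(−92/53) = 30.0% | 2^(−182/53) = 9.3% | 3.2 | 2^(−260/53) = 3.3% |

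The ratio compares the most exposed woman the DMT criterion admits with the most exposed woman the ocrelizumab rule admits. The last column shows how little of that dose is left by term.

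**4. What one affected infant would do (illustration only)**

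If the other nine infants were at or above LLN and one infant were low through fetal exposure, 0/10 (0 to 0.308) would read as 1/10 (0.003 to 0.445). Leaving that infant out gives 0/9, upper limit 1 − 0.025^(1/9) = 0.336.

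**The case against.** The strongest reply is that the effect is probably too small to matter. The 11-fold ratio is taken at the earliest point of transfer, for the least favourable dosing date. By term the modelled maternal residual is about 0.1% at 26 days, and the infant is sampled later still, at 6 to 28 weeks of age. Section 1.3 reports an infant exposed to ocrelizumab in the second trimester, a much later fetal exposure, whose B cells were low at birth but normal two months after a postpartum dose. Nothing in the documents shows that an infant of the kind described here would be below LLN. This stands, and it limits the size of the point. It does not close the gap: the case is a single infant, and its normal value was not taken at Day 30.

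There are also partial backstops. The investigator may exclude a mother with secondary immunodeficiency or an infant whose condition would disturb interpretation. Maternal lymphocyte subtypes are measured at screening, infant serum ocrelizumab is measured at Day 30, and Version 4 repeats low infant counts every four weeks. These would help someone reading an individual case. None names earlier B-cell-depleting therapy, sets a threshold, or changes the reported proportion.

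A reader might infer more than the documents support:

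- **That the investigational-agent criterion leaks in the same way.** It does not for exposure shortly before LMP, which it excludes.
- **That a DMT taken after delivery while nursing would enter the co-primary.** The intercurrent event has no lower bound at the infusion, so it removes those B-cell data.
- **That ocrelizumab from a sponsor study escapes the interval.** The 3-month exclusion covers all ocrelizumab.
- **That the protocol claims to remove all fetal anti-CD20 exposure.** Section 3.3.2 speaks only of ocrelizumab. Extending it to other agents is an inference from the shared mechanism.

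**Conclusion.** The point holds as a narrow gap in eligibility and analysis. A marketed or off-label B-cell-depleting antibody other than ocrelizumab, given shortly before LMP, meets no named exclusion, and no planned analysis of the Day 30 proportion isolates the infant concerned.

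The likely effect is small. Under the 26-day assumption the residual is about 8.6% against 0.8% at LMP+91 days, an 11-fold difference (3-fold at 53 days, 23-fold at 20 days), but only about 0.1% at 37 weeks (0.01% to 3.3% over the same half-lives). Any bias would push the proportion below LLN upward, overstating a lactation effect and not hiding one. The documents give no count of such women, and it may be zero. A shift from 0/10 to 1/10 shows how sensitive the estimate is; it is not an expected result.

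The conclusion rests on ocrelizumab's half-life being a fair stand-in for other anti-CD20 antibodies and on the protocol's own statement about first-trimester placental transfer. It is worth acting on because the remedy is cheap, not because the co-primary is likely to be wrong.

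**What to change.** - **Protocol 4.1.2 and synopsis.** Reconcile the DMT criterion with the fetal-exposure rationale in Section 3.3.2, so that the text addresses B-cell-depleting agents other than ocrelizumab before LMP. Which agents and what interval are for the sponsor's clinical team to decide; none is proposed here.
- **SAP 4.4.4.** Flag each infant whose mother received another B-cell-depleting agent before LMP, and report the Day 30 proportion below LLN with its Clopper-Pearson interval with and without flagged infants. If none is flagged, say so. This part works whatever the enrolment status.

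The flag can be built from the DMT types and time from last DMT to LMP already planned in SAP 4.3.1. One check is needed: that timing refers to the last DMT, so the dates of an earlier B-cell depleter followed by another agent should be confirmed as available.

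The cost is a slightly narrower pool of women starting ocrelizumab, and one extra analysis on fewer infants: for example, 0/9 has an upper limit of 33.6% against 30.8% for 0/10. No new sample or visit is required.

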### Exclusions related to the infant

- Infant is > 24 weeks of age at the time of the mother's first postpartum dose of ocrelizumab
- Infant has any abnormality that may interfere with breastfeeding or milk absorption, including but not limited to cleft palate and/or lip, congenital diaphragmatic hernia and esophageal atresia
- Infant has an active infection. Infant may be included once the infection resolves
- Infant has any other medical condition or abnormality that, in the opinion of the investigator, could compromise the infant's ability to participate in this study, including interference with the interpretation of study results
- Infant has at least one documented BRUE, as defined by the 2016 Guidelines of the American Academy of Pediatrics

